## List of abbreviations

---

AKT	Protein kinase B
BNP	B-type natriuretic peptide
CBC	Complete blood count
CCGs	CRF Completion Guidelines
CDISC	Clinical Data Interchange Standards Consortium
CFR	Code of federal regulations
CI	Confidence interval
CLOVES	Congenital lipomatous overgrowth, vascular malformations, epidermal nevi, scoliosis/skeletal and spinal syndrome
CRF	Case report/record form
CRO	Contract research organization
CT	Computerized tomography
CTCAE	Common Terminology Criteria for Adverse Events
DMP	Data management plan
ECG	Electrocardiogram
ECOG	Eastern Cooperative Oncology Group
eCRF	Electronic case report/record form
EDC	Electronic data capture
ER	Emergency room
FAO	Fibroadipose overgrowth
FIL	Facial infiltrating lipomatosis
GPP	Guidelines for Good Pharmacoepidemiology Practices
HHML	Hemihyperplasia multiple lipomatosis syndrome
HRU	Healthcare resource use
ICMJE	International Committee of Medical Journal Editors
IC50	The half maximal inhibitory concentration
IEC	Independent Ethics Committee
IQR	Interquartile range
IRB	Institutional review board
KTS	Klippel-Trenaunay syndrome
LFT	Liver function tests
MAP	Novartis managed access program
MAR	Missing at random
MCAP	Megalencephaly capillary malformation syndrome
MedDRA	Medical dictionary for regulatory activities
MRI	Magnetic resonance imaging
mTOR	Mammalian target of rapamycin
PASS	Post authorization safety study
PI3K	Phosphatidylinositol-3-kinase
PROS	PIK3CA-related overgrowth spectrum
SAP	Statistical analysis plan
SD	Standard deviation
SDTM	Study data tabulation model
STROBE	Strengthening the Reporting of Observational Studies in Epidemiology
U&E	Urea and Electrolytes

---

## 1 Responsible parties

N/A

## 2 Abstract

Title	Retrospective chart review study of patients with PIK3CA-Related Overgrowth Spectrum (PROS) who have received alpelisib as part of a compassionate use program (EPIK-P1)
Version and date	Final: 04-May-2020
Name and affiliation of main author	PPD : PPD , Novartis
Rationale and background	
See Section 4 for additional information.
 
PROS describes a group of rare syndromes characterized by malformations and tissue overgrowth caused by somatic mutations in the PIK3CA gene. PROS is characterized by a high degree of inter-individual phenotypic heterogeneity attributed to the location and extent of overgrowth and degree of vascular complications.
 
There is currently no approved pharmacological treatment for PROS; available treatment options are represented by de-bulking surgery, amputation, and/or endovascular occlusive procedures.
 
Alpelisib has demonstrated antitumor activity in a variety of cancer cell lines, particularly those harboring PIK3CA mutations and in xenograft models with mutated or amplified PIK3CA.
 
Venot et al. (2018) described the effectiveness of alpelisib in improving disease symptoms among nineteen patients with PROS receiving treatment under a compassionate use program. In these patients, previously intractable vascular malformations and overgrowths became smaller, congestive heart failure was improved, hemihypertrophy was reduced, and scoliosis was attenuated. The treatment was not associated with substantial side effects. This series of cases provides the first direct evidence supporting PIK3CA inhibition as a promising therapeutic option in patients with PROS.
 
Novartis is sponsoring a managed access program (MAP) to allow treatment with alpelisib for patients with PROS. As of November 2019, 65 patients with PROS were expected to be treated with at least one dose of alpelisib at least 24 weeks prior to the planned cut-off date. Given the existing data in this very rare disease setting, Novartis will conduct a retrospective medical chart review to assess changes in clinical and functional outcomes as well as safety in patients with PROS treated with alpelisib.

Research objectives	
See Section 5 for additional information.
 
Primary objective
 
 
1. To describe the efficacy of alpelisib as measured by the proportion of patients with response (yes/no) at Week 24 (+/- 4 weeks), defined by achieving at least a 20% reduction from index date in the sum of measurable target lesion volume (1 to 3 lesions, via central review of imaging scans), provided that none of the individual target lesions have <math>\geq 20\%</math> increase in volume from index date and in absence of progression of non-target lesions and without new lesions (see Section 6.3 for additional information).
 
 
Secondary objectives
 
 
1. To assess changes in the sum of measurable target lesion (1 to 3 lesions) volume over time
 
2. To assess changes in the sum of all measurable (target and non-target) lesion volume over time
 
3. To assess changes in the sum of all measurable non-target lesion volume over time
 

	
 
4. To assess the duration of response defined as time from first documented response to the date of the first documented disease progression or death due to any cause.
 
5. To assess type of medication and non-drug therapies (e.g., concomitant PROS-related medications, PROS-related surgeries, duration of treatment/response) over time
 
6. To assess changes in PROS symptoms and complications (e.g., chronic bleeding/leaking, pain) over time
 
7. To assess changes in functional status (e.g., work/school/pre-school attendance, mobility) over time
 
8. To assess changes in Healthcare Resource Use (HRU; e.g., ER visits, hospitalizations) over time
 
9. To assess changes in clinical assessments such as laboratory evaluation, vital signs and physical findings over time
 
10. To assess the safety and tolerability of alpelisib
 

Study design	
See Section 6.1 for additional information.
 
This study will be a site-based retrospective non-interventional medical chart review of pediatric and adult male and female patients with PROS who initiated alpelisib at least 24 weeks before the cut-off date at a MAP site. The study cut-off date is 09-Mar-2020.
 
Patient-level data will be abstracted from medical charts of all eligible patients at all participating sites. The pre-index (pre-baseline) period will be defined as the period from up to 24 weeks prior to the index date (baseline) through one day prior to the index date. The index date (baseline) is defined as the date of alpelisib initiation. The study period is the period from the index date up to the most recent data available at the time of the cut-off date (Figure 6-1).
 
Information from patients treated with alpelisib will be used to describe the efficacy and safety of alpelisib in patients with PROS.

Setting and study population	
See Section 6.2 for additional information.
 
Patients will be included in this study if they meet all of the following inclusion criteria:
 
 
• Patient (adult or pediatric) is <math>\geq 2</math> years of age*
 
• Patient has a physician confirmed/documented diagnosis of PROS*
 
• Patient has documented evidence of a mutation in the PIK3CA gene*
 
• Patient's condition was assessed by the treating physician as severe or life-threatening and treatment was deemed necessary*
 
• Patient has been treated with at least one dose of alpelisib, initiated on or before 23-Sep-2019 (ie: at least 24 weeks before the cut-off date of 09-Mar-2020)
 
• Patient has medical chart history available during enrollment in the MAP
 
• Patient (in case of pediatric patients assent and/or parent/guardian consent) consented to participate in the study (as required by local ethics regulations)
 
 
*Inclusion criteria for MAP enrollment (assessed at the time of alpelisib initiation).

Study endpoints and variables	
See Section 6.3 for additional information and list of variables
 
Primary endpoint*
 
 
1. Proportion of patients with response (yes/no) at Week 24 (+/- 4 weeks), defined by achieving at least 20% reduction from index date in the sum of measurable target lesion volume (1 to 3 lesions, via central review of imaging scans), provided that none of the individual target lesions have <math>\geq 20\%</math> increase from index date and in absence of progression of non-target lesions and without new lesions (see Section 6.5 for additional information).
 
 
*Target lesion volume may not be available for all patients (see Section 6.9 for additional information).
 
Secondary endpoints
 
 
1. Percent change in the sum of measurable target lesion (1 to 3 lesions) volume, as assessed by a central review of imaging scans, as measured by the change between the index date and key time-points following the index date
 
2. Percent change in the sum of all measurable (target and non-target) lesion volume, as assessed by a central review of imaging scans, as measured by the change between the index date and key time-points following the index date
 
3. Percent change in the sum of all measurable non-target lesion volume, as assessed by a central review of imaging scans, as measured by the change between the index date and key time-points following the index date
 
4. Duration of response defined as the time from first documented response, to the date of the first documented disease progression or death due to any cause.
 
5. Change in type of medication and non-drug therapies (e.g., concomitant PROS-related medications, PROS-related surgeries, duration of treatment/response) over time
 
6. Change in PROS symptoms and complications
 
7. Change in functional status
 
8. Change in HRU
 
9. Change in clinical assessments such as laboratory evaluation, vital signs and physical findings over time
 
10. Type, frequency, seriousness, and severity per CTCAE v4.03 criteria and causality assessments of treatment-emergent adverse events
 

Data source	
See Section 6.4 for additional information.
 
The data for this study will be retrospectively abstracted from medical charts of eligible patients with PROS treated at participating clinical sites.
 
Collected data will be converted to conform to CDISC data standards for electronic submissions.

Study size	
See Section 6.6 for additional information.
 
This study aims to collect medical chart information on eligible patients with PROS at participating sites, including all patients who have been treated with alpelisib. As a result, no formal sample size calculation has been performed.
 
As of November 2019, 65 patients with PROS were expected to be treated with at least one dose of alpelisib at least 24 weeks prior to the planned cut-off date and will be potentially included in the trial.

Data analysis	
See Section 6.8 for additional information.
 
All analyses will be pre-specified in the statistical analysis plan (SAP). The primary and secondary analyses for this study will be descriptive in nature (estimation based), and therefore no hypothesis testing will be conducted. The data abstracted in this study will be summarized as appropriate. Descriptive analyses will be conducted where continuous data will be summarized by measures that may include the mean, SD, median, interquartile range (IQR), minimum, and maximum. Categorical and binary data will be presented by frequency counts and percentages. All descriptive analyses will be presented along with their 95% CIs as appropriate.
 
The primary endpoint will be summarized and reported for the following subgroups: age, mutation type, lesion tissue type, and PROS subtype.

### **3 Amendments and updates**

#### **Amendment 01 (04-May-2020)**

##### **Amendment rationale**

No patients have been enrolled and no patients are planned to be enrolled until after this amendment is approved and in place.

The changes implemented in this protocol amendment include the specification of a cut-off date (09-Mar-2020) in order to define the sample of patients to be enrolled in the study. This approach will allow Novartis to minimize the impact of the SARS-CoV-2 (COVID-19) pandemic on study integrity.

The cut-off date definition was changed to avoid missing data due to the COVID-19 pandemic. In the original protocol, the cut-off date was defined as the date of the start of data entry (the data abstraction date). This amendment changes the cut-off date for the study to a fixed date of 09-Mar-2020. The assessment of response status is not expected to be impacted as all patients initiated alpelisib at least 24 weeks before 09-Mar-2020. This results in inclusion criteria number 5 being updated.

Following discussion with FDA, the primary analysis is modified. In the original protocol, the primary analysis was applying imputation of the missing volumetric assessments for target lesions at Week 24 (+/- 4 weeks), while in the current version of the protocol a complete case analysis is utilized.

The complete case analysis is planned to be performed based on patients without missing response as defined in [Section 6.8.1](#).

The analysis using imputed data will be performed as sensitivity analysis (instead of as primary analysis).

Duration of response is added to the secondary objectives as it is considered an important measure for the assessing benefit of the study drug.

Analysis of the secondary endpoints: for the endpoints related to objective #8, growth and development information were added to better characterize clinical assessments in patients who were aged <18 years at the time of alpelisib initiation.

The primary endpoint will also be summarized and reported by sex.

To ensure consistent selection criteria, the target lesion selection will be performed by the independent central reviewer instead of the investigator.

Typographical and grammatical errors are corrected, and text has been reworded to add clarity where required.

##### **Changes to the protocol**

Changes to specific sections of the protocol are shown in the track changes version of the protocol using strike through red font for deletions and red underline for insertions.

List of major change(s) that are made to the protocol:

- [Abstract](#): Added new secondary objective (#4) for duration of response. Cut-off date changed from the abstraction date to 09-Mar-2020 for all patients. Index date noted as equivalent to baseline.
- [Section 5.2](#): Added new secondary objective (#4) for duration of response.
- [Section 6.1](#): Cut-off date updated from the date of abstraction to 09-Mar-2020 for all patients; rationale for the cut-off date change is provided. Definition of pre-index date period is further clarified. Index date noted as equivalent to baseline.
- [Section 6.2.1](#): Inclusion Criteria 5 is updated; inclusion criteria 5 changes the abstraction date to the cut-off date (09-Mar-2020).
- [Section 6.3](#): The cut-off date for the retrospective data collection has been updated from the start date of data abstraction to a universal cut-off date for all patients, 09-Mar-2020. The term “end of follow-up” is updated to “end of study”. The Definition of “end of study” is clarified. Clarified that the eCRF will collect reasons for missing data for the Week 24 lesion assessment.
- [Table 6-1](#): the word “end of follow up” has been changed as “end of study” and some wording has been added to clarify the time window around the last observation.
- [Section 6.3.1](#): Patients who permanently discontinue alpelisib prior to 24 weeks of treatment and patients who required surgery as rescue therapy between index date and 24 weeks of treatment are defined as non-responders.
- [Section 6.3.2](#): Secondary endpoint (#4) added for duration of response.
- [Section 6.5](#): Name of imaging charter updated to “Independent Central Review Charter”. Selection of target lesions changed from investigator responsibility to central reviewer responsibility.
- [Section 6.7](#): Corrected the abstraction process to data entry instructions.
- [Section 6.8.1](#): Target lesion selection was updated from the investigator selecting the target lesion(s) to the central reviewer selecting the target lesion(s). Redundant text is removed. Criteria defining non-responders were added. Definition of non-responders and missing response were added.
- [Section 6.8.1.1](#): Sex added as criteria for a subgroup analysis.
- [Section 6.8.2](#): Analysis of the secondary endpoints: for the endpoints related to objective #8, growth and development information were added to better characterize clinical assessments in patients who were aged <18 years at the time of alpelisib initiation. Duration of response was added as a secondary objective. Example intervals were updated. Severity clarified as toxicity grade. Text reworded for clarity. Examples updated to reflect eCRF design. Adverse events will be coded using the Medical dictionary for regulatory activities (MedDRA) terminology. The latest available MedDRA version at the time of the analyses will be used.
- [Section 6.9](#): changed planned analysis from imputation method to complete case analysis
- [Section 6.10.1](#): Data validation plan updated to data management plan or equivalent.

The changes to the protocol are considered to be substantial. This assessment is made to comply with the European legislation (Directive 2010/C 82/01/EC).

## IRBs/IECs

A copy of this amended protocol will be sent to the Institutional Review Board (IRBs)/Independent Ethics Committee (IECs) and Health Authorities.

The changes described in this amended protocol require IRB/IEC approval prior to implementation.

The changes herein do not affect the Informed Consent.

## 4 Rationale and background

PROS describes a group of rare syndromes characterized by malformations and tissue overgrowth caused by somatic mutations in the PIK3CA gene.

The umbrella term PROS encompasses a group of syndromes with diverse phenotypes, including (but not limited to) CLOVES, MCAP, HHML, FAO, hemimegalencephaly, FIL, KTS, and others.

In PROS, individuals' malformations are seen as overgrowth in several different tissues such as skin, vasculature, bone, fat, and brain tissue depending on the specific disease. Some of the malformations are congenital malformations of the vasculature causing excessive immature vasculature tissue, which may or may not be associated with overgrowth of other tissue. PROS is characterized by a high degree of inter-individual phenotypic heterogeneity attributed to the location and extent of overgrowth and degree of vascular complications. The rate and timing of excess growth is also variable, sometimes limited to childhood, while other patients have progressive soft tissue overgrowth during adult life. These rare conditions have no approved medical treatment and are associated with a number of complications which depend on the anatomical site and extent of overgrowth and vascular malformations. These complications may include functional impairment (e.g., impairment in walking or activities of daily living), pain, recurrent superficial infections, thromboembolism, bleeding and/or organ dysfunction, all of which may be debilitating, and cause early morbidity and even mortality (Parker et al. 2019). Current treatment includes surgical de-bulking procedures and amputation, and interventional procedures including sclerotherapy, laser and/or endovascular occlusive procedures. Regrowth following surgery occurs frequently and can require repeated surgery.

Sirolimus is an mTOR inhibitor that was introduced in 2011 as the first pharmacologic treatment for complicated vascular anomalies.

Sirolimus treatment has been shown to sequester components of mTORC2, which acts upstream on AKT signaling. However, it has not always been associated with lesion size reduction and has significant side effects, which include immunosuppression (Le Cras et al. 2019).

Alpelisib is an oral  $\alpha$ -specific class I PI3K inhibitor belonging to the 2-aminothiazole class of compounds. In biochemical assays, alpelisib potently inhibits the p110 $\alpha$  subunit of PI3K (IC50 = 4.6 nM)  $\geq$  50-fold compared to the other class I PI3K isoforms (e.g., p110 $\beta$  IC50 = 1156 nM, p110 $\delta$  IC50 = 290 nM, p110 $\gamma$  IC50 = 250 nM), and it is inactive against most other kinases (Fritsch et al. 2014). Alpelisib has demonstrated antitumor activity in a variety of cancer cell lines, particularly those harboring PIK3CA mutations and in xenograft models with mutated or amplified PIK3CA (Keegan et al. 2018). Clinical studies have also demonstrated the antitumor

activity of alpelisib, especially in tumors with PIK3CA alterations, with a favorable safety profile (Juric et al. 2019, Hoste et al. 2018).

Venot et al. (2018) described a postnatal mouse model of PROS/CLOVES that partially recapitulates the human disease. The model demonstrated the efficacy of alpelisib in preventing and improving organ dysfunction. The publication also describes how alpelisib was used in a compassionate use program to treat 19 patients (adult and pediatric) with PROS. This publication describes improvement in the disease symptoms in all patients receiving alpelisib treatment. Previously intractable vascular malformations became smaller, clinical complications such as congestive heart failure, hemihypertrophy and scoliosis improved. As reported in the publication, the treatment was not associated with substantial adverse effects. This series of cases provides the first direct evidence supporting PIK3CA inhibition as a promising therapeutic option in patients with PROS. It should also be noted that the 19 patients described in this publication are also intended to be included in this study through abstraction of data from medical charts into the study database.

Novartis is supporting compassionate use requests to allow for treatment with alpelisib for patients with severe and/or life-threatening PROS as part of an overarching MAP. As of November 2019, this program has approved requests for the treatment of over 100 patients from 14 countries, of which 65 patients were expected to be treated with at least one dose of alpelisib at least 24 weeks prior to the planned cut-off date. Considering the meaningful number of patients that are being treated globally with alpelisib under compassionate use programs in this rare indication, this retrospective chart review will describe clinical and functional outcomes as well as safety in patients with PROS before treatment with alpelisib and at key time-points after treatment initiation.

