#### **6.3.1 Primary endpoint**

The primary endpoint for this study was selected as it is an objective and quantitative outcome measure associated with manifestations of PROS that is observable in a significant proportion of the heterogeneous patient population eligible for inclusion. In addition, it is also associated with clinical benefit in patients with this condition (as documented in the [Venot et al. \(2018\)](#) publication).

1. Proportion of patients with response (yes/no) at Week 24 (+/- 4 weeks), defined by achieving at least 20% reduction from index date in the sum of measurable target lesion volume (1 to 3 lesions, via central review of imaging scans), provided that none of the individual target lesions have  $\geq 20\%$  increase from index date and in absence of progression of non-target lesions and without new lesions.

Patients who permanently discontinue alpelisib prior to 24 weeks of treatment, patients who required surgery as rescue therapy between index date and 24 weeks of treatment and patients with MRI scan performed at Week 24 for which the volumetric measurement cannot be calculated are defined as non-responders.

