## **9 Plans of disseminating and communicating study results**

Upon study completion and finalization of the study report, the results of this non-interventional study may be either submitted for publication and/or posted in a publicly accessible database of results. Publications will comply with internal Novartis standards and the International Committee of Medical Journal Editors (ICMJE) guidelines. In addition, results obtained from the current study are intended for submission as primary data to health authorities worldwide.

No individual investigator may publish on the results of this study without prior approval from Novartis.

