Alpelisib is an oral α -specific class I PI3K inhibitor belonging to the 2-aminothiazole class of compounds. In biochemical assays, alpelisib potently inhibits the p110 α subunit of PI3K (IC₅₀ = 4.6 nM) \geq 50-fold compared to the other class I PI3K isoforms (e.g., p110 β IC₅₀ = 1156 nM, p110 δ IC₅₀ = 290 nM, p110 γ IC₅₀ = 250 nM), and it is inactive against most other kinases (Fritsch et al 2014). Alpelisib has demonstrated antitumor activity in a variety of cancer cell lines, particularly those harboring PIK3CA mutations and in xenograph models with mutated

or amplified PIK3CA (Keegan et al 2018) Clinical studies have also demonstrated the antitumor activity of alpelisib, especially in tumors with PIK3CA alterations, with a favorable safety profile (Juric et al 2019, Hoste et al 2018).

Venot et al (2018) described a postnatal mouse model of PROS/CLOVES that partially recapitulates the human disease. The model demonstrated the efficacy of alpelisib in preventing and improving organ dysfunction. The publication also describes how alpelisib was used in a compassionate use program to treat 19 patients (adult and pediatric) with PROS. This publication describes improvement in the disease symptoms in all patients receiving alpelisib treatment. Previously intractable vascular malformations became smaller, clinical complications such as congestive heart failure was improved, and hemihypertrophy and scoliosis was improved. As reported in the publication, the treatment was not associated with substantial adverse effects. This series of cases provides the first direct evidence supporting PIK3CA inhibition as a promising therapeutic option in patients with PROS. It should also be noted that the 19 patients described in this publication are also intended to be included in this study through medical charts into the study database.

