3.5.4 Subgroup analyses for the primary endpoint

The primary endpoint will be summarized and reported for the following subgroups:

- Age (e.g., 2-5; 6-11;12-17; 18+; pediatric patients and adults patients)
- Sex
- Mutation type (e.g., frequent, less frequent)
- PROS subtype (e.g., CLOVES, KTS)
- Lesion type (e.g., vascular, adipose)

Forest plots (Response %, 95% CI) will be produced to graphically depict the treatment effect estimates in different subgroups.

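### The 19 patients of the published series that prompted the study are to be pooled with the other patients, and the visible SAP has no analysis that separates them

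*Protocol*

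**What the plan says.** Protocol section 4 describes a published compassionate-use series of 19 patients. Of its results it says "This publication describes improvement in the disease symptoms in all patients receiving alpelisib treatment", and it adds that malformations shrank. It then concludes: "This series of cases provides the first direct evidence supporting PIK3CA inhibition as a promising therapeutic option in patients with PROS". The same section says that "the 19 patients described in this publication are also intended to be included in this study", and SAP section 1.1 repeats the intention.

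Protocol section 6.3.1 first justifies the primary endpoint as objective, quantitative and observable in a significant proportion of a heterogeneous population. It then adds that "it is also associated with clinical benefit in patients with this condition", citing the same publication.

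Protocol section 6.1 pools all eligible patients from all sites, and section 6.2.2 lists no exclusion criteria. SAP section 3.5.4 states "The primary endpoint will be summarized and reported for the following subgroups" and lists age, sex, mutation type, PROS subtype and lesion type. The sensitivity analyses in SAP section 3.5.3 are multiple imputation and best/worst case; both deal with missing response only.

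Protocol section 9 says that "results obtained from the current study are intended for submission as primary data to health authorities worldwide".

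**The concern.** A series that supplies the reason for a study, and part of the reason for its endpoint, is not fresh evidence when it is counted again in that study's estimate. The overlap is disclosed, but nothing in the visible plan lets a reader see how far the response rate depends on it. The bias discussion in Protocol section 6.11 covers selection from the managed access program and independent radiology, not overlap with the published series.

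What is at stake is interpretation. A health authority given the pooled rate as primary data would want to know whether it also holds in patients not previously reported. No hypothesis is tested, so type I error is not at issue.

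**Working it through.** **The plan's own figure.** Protocol Table 6-2 gives exact 95% intervals at n = 50. Two-sided Clopper-Pearson limits for 10, 15, 20 and 25 responders of 50 are 0.100–0.337, 0.179–0.446, 0.264–0.548 and 0.355–0.645. All four rows match to three decimals, with widths of 0.237 to 0.289.

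**Share of the 19.** Protocol section 6.6 expects about 65 eligible patients and uses 50 after refusals.
- Of those eligible: 19/65 = 0.292.
- Of the assumed participants: 19/50 = 0.38.

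Neither is the share of the primary analysis set. Membership of that set also needs a target lesion, a baseline scan and a non-missing response (SAP sections 3.2 and 3.5.1). These rules can remove series patients and others at different rates, so the share could be lower or higher.

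**Effect on the pooled rate.** Let k be the series patients analysed, q their response rate, p the rate in the others and N the total.

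Pooled rate = [k·q + (N − k)·p] / N

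Shift relative to p = (k/N)·(q − p)

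The documents give neither q nor p, so both are assumptions. With k = 19, N = 50 and p = 0.30, the 31 others contribute 31 × 0.30 = 9.3:

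| q (assumed) | Pooled rate | Shift |
|---|---|---|
| 0.20 | (3.8 + 9.3)/50 = 0.262 | −0.038 |
| 0.30 | (5.7 + 9.3)/50 = 0.300 | 0 |
| 0.40 | (7.6 + 9.3)/50 = 0.338 | +0.038 |
| 0.60 | (11.4 + 9.3)/50 = 0.414 | +0.114 |
| 0.80 | (15.2 + 9.3)/50 = 0.490 | +0.190 |

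If all 65 take part, the factor k/N falls from 0.38 to 0.29. At q = 0.80 the shift is then 0.292 × 0.50 = +0.146.

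**What a reader could miss.** Take q = 0.80 and p = 0.30 in whole patients: 15/19 and 9/31. The pooled result is 24/50 = 0.48 (95% CI 0.337–0.626), against 9/31 = 0.29 (0.142–0.480) in the others alone. The planned tables would show only the first.

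**Precision of separate estimates (Clopper-Pearson).**

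| Responders | Rate | 95% CI | Width |
|---|---|---|---|
| 6/31 | 0.194 | 0.075–0.375 | 0.300 |
| 9/31 | 0.290 | 0.142–0.480 | 0.338 |
| 12/31 | 0.387 | 0.218–0.578 | 0.360 |
| 16/31 | 0.516 | 0.331–0.698 | 0.368 |
| 10/19 | 0.526 | 0.289–0.756 | 0.467 |

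**The case against.** The strongest defence is that a study of all eligible treated patients should include these 19, and that dropping them would itself be a selection. Protocol section 6.11 says that every program patient who started at least 24 weeks earlier will be contacted, without pre-selection. This stands, and it is why the pooled analysis should remain primary.

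A reader might go further and infer one of the following. The documents do not support any of them.
- *The 19 were chosen because they did well, so the pooled rate is inflated.* Protocol section 6.2 calls them the initial patients treated under French compassionate-use rules, and section 4 reports improvement in all of them. Both statements fit an unselected first cohort.
- *Their published success carries over to the primary endpoint.* The publication is cited for symptom improvement and shrinkage. The endpoint is a centrally read reduction of at least 20% in summed target volume, and it also requires no progression, no new lesions, no early discontinuation and no rescue surgery. Target lesions are to be chosen centrally before later images are assessed (Protocol section 6.5). Central reading limits measurement bias, but it does not make these patients new evidence.
- *The other patients form a prospective validation set.* This is a chart review. The amended protocol is dated 04-May-2020, after the 09-Mar-2020 cut-off, so every patient's course up to the cut-off had already happened. The distinction is only between patients already reported and patients not previously reported.
- *All 19 will be in the primary estimate.* Inclusion is intended. Consent, eligibility and the analysis-set rules still apply.

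It is also fair to say that a split would seldom be decisive. The intervals are wide, and the 19 were the earliest treated and were all treated in France, so any difference is confounded with country and calendar time.

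**Conclusion.** The point holds as one of transparency, not as a demonstrated bias. The response rate partly reuses the data that prompted the study, and the visible SAP offers no way to see the rate without those data. Because parts of the SAP are redacted, the absence is confirmed for the visible text only.

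The series could be a substantial part of the sample, at 29% of the expected eligible patients or 38% of the assumed participants. The effect on the estimate is unknown in both size and direction. Under the assumptions used above it runs from about −4 to +19 percentage points and is zero when the two groups respond alike. These scenarios rest on all 19 being among 50 analysed patients and on assumed response rates; they are not predictions.

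**What to change.** Keep the pooled primary analysis as it is.
- In SAP section 3.5.4, add a subgroup for inclusion in the published case series (yes/no).
- In SAP section 3.5.3, add a sensitivity analysis of the primary endpoint that excludes the series patients.
- Give both with two-sided 95% Clopper-Pearson intervals. State the number of series patients in the full study population, the efficacy population and the complete-case set, so that the actual share is visible.
- State in advance that the comparison is descriptive and is confounded with country and calendar time.

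The cost is one flag variable and a few table rows. The price in precision is an interval width of about 0.30–0.37 at n = 31, against 0.24–0.29 at n = 50, and about 0.47 in the series itself (at 10/19). The addition is cheap and useful, but it will seldom settle whether the two groups differ.
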